### **Serious Adverse Event Reporting (SAE)**

A serious adverse event is – any adverse drug experience occurring at any dose that results in any of the following outcomes:

- Death
- A life-threatening adverse drug experience – any adverse experience that places the patient, in the view of the initial reporter, at immediate risk of death from the adverse experience as it occurred. It does not include an adverse experience that, had it occurred in a more severe form, might have caused death.
- Inpatient hospitalization or prolongation of existing hospitalization
- A persistent or significant disability/incapacity – a substantial disruption of a person's ability to conduct normal life functions.
- A congenital anomaly/birth defect.

Important medical events that may not result in death, be life-threatening, or require hospitalization may be considered a serious adverse drug experience when, based upon appropriate medical judgment, they may jeopardize the patient or subject and may require medical or surgical intervention to prevent one of the outcomes listed in this definition. Examples of such medical events include allergic bronchospasm requiring intensive treatment in an emergency room or at home, blood dyscrasias or convulsions that do not result in inpatient hospitalization, or the development of drug dependency or drug abuse (21 CFR 312.32).

- Important medical events as defined above, may also be considered serious adverse events. Any important medical event can and should be reported as an SAE if deemed appropriate by the Principal Investigator or the IND Sponsor, Office of Research Education and Regulatory Management (ORERM).

- All events occurring during the conduct of a protocol and meeting the definition of a SAE must be reported to the IRB in accordance with the timeframes and procedures outlined in "University of Texas M. D. Anderson Cancer Center Institutional Review Board Policy on Reporting Serious Adverse Events". Unless stated otherwise in the protocol, all SAEs, expected or unexpected, must be reported to ORERM, regardless of attribution (within 5 working days of knowledge of the event). Hospitalizations for the management of any expected adverse events (previously described) will not have an expedited report but it will be included in the annual report via the SAE log.
- **All life-threatening or fatal events**, expected or unexpected, and regardless of attribution to the study drug, must have a written report submitted within **24 hours** (next working day) of knowledge of the event to the Safety Project Manager in ORERM.
- The MDACC "Internal SAE Report Form for Prompt Reporting" will be used for reporting to ORERM.
- Serious adverse events will be captured from the time the patient signs consent until 30 days after the last dose of drug. Serious adverse events must be followed until clinical recovery is complete and laboratory test have returned to baseline, progression of the event has stabilized, or there has been acceptable resolution of the event.
- Additionally, any serious adverse events that occur after the 30 day time period that are related to the study treatment must be reported to ORERM. This may include the development of a secondary malignancy.

(Please see **Appendix E** regarding data capturing of adverse events and adverse events source documentation.)

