### **2.3 Rationale for the Study Design**

Due to its clinical safety, rituximab is widely used in combination with various cytotoxic agents. Treatments using combinations of rituximab with cytoreductive combination chemotherapy, like CHOP (a combination of cyclophosphamide, doxorubicin, vincristine, and prednisone), hyper-CVAD, or fludarabine-cyclophosphamide are highly active. However, such combinations of chemoimmunotherapy also suffer from various systemic toxicities associated with the non-targeted nature of chemotherapy. Thus, studies of targeted therapy combinations like CMC-544 (target CD22) and rituximab (targets CD20) in pre-B ALL would be highly attractive, because of the potential of high efficacy and low toxicity. This is the purpose of this study. If successful, this combined targeted therapy may become a new standard of care for patients with refractory relapsed ALL. It may also be brought into frontline therapy of minimal residual disease to increase the

cure of patients with newly diagnosed pre-B ALL. Thus the study has major potential therapeutic implications for improving adult ALL prognosis.

The phase I-II studies of CMC-544 determined the phase II dose to be 1.8 mg/m^2 once every 3-4 weeks. The DLT was myelosuppression. Other side effects were gastrointestinal and hepatic. Only 1 case of veno occlusive disease was noted among 176 patients treated(14). Phase II studies combining rituximab 375 mg/m^2 on Day 1 and CMC-544 1.8 mg/m^2 on Day 2 were safe and effective in lymphomas(15).

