#### **2.4      Update of October 6, 2010**

At present, a total of 21 patients with refractory relapse ALL have been treated. Fifteen of them were in second salvage or worse; eight of them have translocation 4;11 or Philadelphia positive ALL. Overall, 12 of 21 patients have achieved either CR (n=5) or Cri (n=7), for an overall response rate of 57%. This is even better than what is expected using standard combination intensive chemotherapy in first salvage, with which the CR rate would be expected to be about 30%. Toxicity has been minimal. There were two episodes of tumor lysis responding to standard measures. Fever on Day 2 post therapy is common. Transient grade 1-3 elevations of liver enzymes have been observed, which are expected and self-limited. Two patients died within four weeks, one of them with progressive disease. Overall the treatment appears to be extremely effective with minimal toxicity. This has allowed so far at least 4 patients to undergo allogeneic stem cell transplant. Based on the findings we propose to 1) allow treatment of patients in first salvage regardless of the duration of first CR, and 2) increase the total number of

patients to 60 to allow more accurate assessment of the overall response rate and define more precisely predictive factors for response to therapy.

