## **2.6 Update of December 2, 2011**

This study has completed accrual of 20 patients on the weekly schedule. The early analysis shows encouraging results with trends for similar or better efficacy and less

toxicity. Among the first 15 evaluable patients, 2 achieved CR (12%), 5 achieved CRp (31%) and 1 achieved CRi (6%). Thus, 8 of 15 evaluable patients (53%) achieved marrow CR. Five of the 7 evaluable responders (71%) achieved MRD negativity. Three patients underwent allogeneic SCT; no VODs were noted. Transient liver enzyme elevations grade 1-2 were noted in 5 of 20 (25%), severe in 2.

In discussions with Pfizer, we emphasized the importance of these findings but the limited number of patients makes definite conclusions difficult. It was agreed to increase the number of treated patients on the weekly schedule by another 20, for a total of 40 patients, to assess more precisely the response and toxicity profile compared with the 49 patients treated with the single dose every 3-4 weeks.

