## **7.1 Post Treatment Evaluation**

Patients will be evaluated 30 days post receiving the last treatment of CMC-544 to collect information regarding toxicity unless the patient receives further therapy. This could be done during a regular clinic or inpatient visit or by phone call (research nurse or physician) if patient cannot be physically present at MD Anderson.

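### Veno-occlusive disease after transplant can be under-counted, because no scheduled toxicity contact follows transplant and SAEs beyond 30 days need reporting only if judged related

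*Combined protocol and SAP*

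**What the plan says.** **Why VOD matters here.** Section 1.0 makes side effects one of two objectives. Section 2.3 reports: "Only 1 case of veno occlusive disease was noted among 176 patients treated". Section 3.2.1 also lists VOD among adverse reactions in the first-in-human study. Section 2.6 says of the weekly schedule: "Three patients underwent allogeneic SCT; no VODs were noted". It then adds 20 patients, for a total of 40, to describe response and toxicity more precisely against the 49 single-dose patients. For the single-dose schedule, Section 2.4 says "This has allowed so far at least 4 patients to undergo allogeneic stem cell transplant" and gives no VOD result for them.

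**How toxicity is collected after treatment.**

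- Section 7.1: "Patients will be evaluated 30 days post receiving the last treatment of CMC-544 to collect information regarding toxicity", but not if further therapy is given. This is the only scheduled post-treatment toxicity contact.
- Section 10.0, SAE window: SAEs are captured from consent to 30 days after the last dose. Unless the protocol says otherwise, all SAEs go to ORERM whatever their attribution.
- Section 10.0, after that window: "any serious adverse events that occur after the 30 day time period that are related to the study treatment must be reported to ORERM".
- Section 10.0, life-threatening or fatal events: a written report within 24 hours, whatever the attribution. This bullet carries no end date of its own.
- Section 10.0, case report form (CRF): it receives unexpected adverse events only.

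The documents contain no VOD definition, no VOD data item and no toxicity follow-up tied to transplant.

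**The concern.** Transplanted patients are the group in which Section 2.6 itself mentions VOD, and they are also the group in which the collection rules are weakest. Transplant is an obvious rival cause of liver injury, so a rule that depends on attribution works least well in them. A VOD to which the drug contributed can be put down to the transplant and then fall outside what must be reported.

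The VOD rate, part of a stated objective, would then be biased toward zero. If transplant timing or frequency differs between the schedules, the under-count can differ too, which matters for a comparison of their toxicity. With so few transplants, one missed case changes the picture. The point concerns toxicity ascertainment only, not response, durability or survival.

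**Working it through.** **1. When transplant occurs.** The documents do not define further therapy. On the plain reading it includes transplant.

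- Transplant within 30 days of the last dose: the 7.1 contact is waived.
- Transplant later than that: the contact takes place, but before the transplant.

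On either path no scheduled toxicity contact follows the transplant.

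**2. Which rule would catch a VOD.**

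- Serious, within 30 days of the last dose: captured whatever the attribution.
- Not serious, within 30 days: depends on the 7.1 contact, which may be waived, and on a CRF limited to unexpected events. VOD is already described for this drug, so it may be treated as expected.
- Serious, after 30 days, judged related: must be reported.
- Serious, after 30 days, attributed to transplant: no duty to report to ORERM under the 30-day rule. The IRB wording, which covers all SAEs during conduct of the protocol, may be broader.
- Life-threatening or fatal, after 30 days: the 24-hour bullet may apply, or the 30-day window may limit it. The text does not settle this.
- Not serious, after 30 days: no route is described.

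The gap therefore lies mainly after day 30, and in events that are non-serious or treated as expected.

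**3. Size of the bias.** Let p be the true VOD rate in transplanted patients and c the fraction captured. The expected observed rate is p × c, so the shortfall is p × (1 − c). The documents give neither p nor c, so the shortfall cannot be computed. The 1/176 = 0.57% in Section 2.3 (exact 95% interval 0.01% to 3.1%) is not stated to be a rate in transplanted patients and cannot stand in for p.

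As an illustration only, the chance of seeing no VOD in 3 patients is (1 − p × c)³:

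- p = 10%: 73% with full capture; 86% with c = 50%.
- p = 20%: 51% with full capture; 73% with c = 50%.
- p = 30%: 34% with full capture; 61% with c = 50%.

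**4. A separate matter: what 0 of 3 can show.** With full capture, the one-sided 95% upper limit for 0 of n is 1 − 0.05^(1/n). For n = 3 this is 1 − 0.05^(1/3) = 63.2%. The two-sided exact limit is 1 − 0.025^(1/3) = 70.8%. These limits come from having three patients and would be the same with perfect collection, so they do not measure capture bias.

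**5. What 40 weekly patients would give.** Assume the transplant fraction stays at 3/20, taking all patients accrued at the update as the denominator. Then 40 × 3/20 = 6 transplants. With none affected, the limit is 1 − 0.05^(1/6) = 39%. One missed case would be the difference between 0/6 = 0% and 1/6 = 17%.

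**The case against.** A reader might go further and infer that toxicity follow-up is switched off in transplanted patients, so that the plan claims an absence of VOD it cannot support. The documents do not bear this out.

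- Section 7.1 waives one contact, which may be a phone call. It does not waive SAE capture. A serious VOD within 30 days of the last dose must be reported even if blamed on the transplant.
- The life-threatening or fatal bullet and the IRB wording are both independent of attribution and may reach beyond day 30.
- The after-30-day rule states what must be reported. It does not forbid recording other events, and Section 2.6 gives transplants and VOD together, so the investigators were evidently looking.
- The statement in 2.6 is an interim observation. Its denominator of three is in the same sentence, and the next paragraph concedes that the numbers are too small for definite conclusions. Section 11.2 calls the weekly toxicity evaluation descriptive.
- The 63% limit might be read as the size of the capture problem. It is not; it reflects three patients.
- Pooling in the four earlier transplants as though none had VOD is not supported either. Section 2.4 says at least four and gives no VOD result.
- Appendix E and the institutional guidelines were not available and may add rules.

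All of this stands, and it narrows the gap. It does not close it. No text schedules a toxicity assessment after transplant, the duty to report later SAEs to ORERM rests on relatedness, and a known reaction may be left out of the CRF. SAE reports, even when complete, do not yield a count over all transplanted patients.

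**Conclusion.** The point holds as a limited gap in ascertainment. Followed as written, the plan can under-count VOD after transplant, mainly for events more than 30 days after the last dose and for events that are non-serious or regarded as expected. The direction of the bias is downward. Its size cannot be computed from the documents, and nothing in them shows that a case has actually been missed. Separately, 0 of 3 leaves a VOD rate of up to 63% open (one-sided 95%), even with full capture.

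This rests on two assumptions: that transplant counts as further therapy when it falls before the 30-day contact, and that Appendix E does not already require VOD recording after transplant. If Appendix E does, the point reduces to reconciling the texts. It is a cheap improvement worth making for a stated objective, not a flaw that undermines the trial.

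**What to change.** 1. **Section 7.1:** do not waive toxicity recording for patients who go on to transplant. Restoring the day-30 contact alone is not enough, because it does not cover VOD arising later.
2. **Section 10.0:** record VOD (yes/no, date, grade) for every transplanted patient, regardless of attribution or expectedness, to one fixed date after transplant chosen by the investigator, abstracted from the transplant record.
3. **Reporting:** give VOD as n/N transplanted, by schedule, with an exact interval. A further split by number of courses would leave near-empty cells and is not needed.
4. **Reconcile in Section 10.0:** the 30-day window, the IRB wording on SAEs during conduct of the protocol, and the life-threatening or fatal bullet. State which governs after day 30, and check the result against Appendix E.

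Section 2.6 is a dated update and need not be rewritten. The cost is a chart abstraction for a small number of patients and one CRF item, with no added visits or tests and no change to treatment.

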**Reporting to FDA:**

- Serious adverse events will be forwarded to FDA by the IND Sponsor (Safety Project Manager ORERM) according to 21 CFR 312.32.

It is the responsibility of the PI and the research team to ensure serious adverse events are reported according to the Code of Federal Regulations, Good Clinical Practices, the protocol guidelines, the sponsor's guidelines, and Institutional Review Board policy.

## **11.0 Statistical Considerations**

A total of up to 60 patients will be treated. The primary endpoint for efficacy is response which is defined as CR, CRI or PR.

The method of Thall [1995] will be employed to perform interim futility monitoring.

The trial will be stopped early if:  $\Pr[\theta > 0.20 | \text{data}] < 0.10$ . Where  $\theta$  denotes the response rate. That is, given the outcomes from the patients who have already been evaluated, if we determine that there is less than a 10% chance that the response rate is 20% or more, we will stop the trial for futility. We assume a prior distribution of  $\theta \sim \text{beta}(1,1)$ . Stopping boundaries corresponding to this probability criterion are to terminate the trial if:

(# patients with CR, CRi, or PR) / (# patients evaluated)

≤ 0/10, 1/17, 2/24, 3/31, 4/37

The operating characteristics for the futility monitoring rule are shown in the following table.

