## **2.5 Update of January 7, 2011**

At the present update, 38 patients have been treated. Of 32 evaluable patients, 8 achieved CR and 10 achieved CRI or CRp for an overall response rate of 18/32 =56%. Toxicities were reasonable and included Grade 1-2 elevations of liver function tests which were transient. Two patients had Grade 3 liver function abnormalities; the attribution to the drug was questionable.

From preclinical studies, it is thought that lower dose more frequent exposure schedules to inotuzumab may offer better anti-ALL efficacy. Following discussions in the Leukemia group and with Pfizer investigators, it was decided to study a different schedule of inotuzumab given weekly times 3. The total dose per course is the same, 1.8 mg/m^2. The treatment will be with inotuzumab 0.8 mg/m^2 on Day 1, 0.5 mg/m^2 on Day 8, and 0.5 mg/m^2 on Day 15. Courses are given every 3 weeks. When rituximab is required, it will be given weekly with inotuzumab. A total of 20 patients will be treated to gain experience with efficacy and toxicity. Early stopping rules will be implemented for an overall response rate < 40%.

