### **Operating Characteristics for Stopping Rule (PL=0.10)**

Clinical Scenario	Early Stopping Probability	Achieved Sample Size (25th, 50th, 75th percentile)
Response rate is 0.1	0.79	10, 17, 37
Response rate is 0.2	0.24	40, 40, 40
Response rate is 0.3	0.044	40, 40, 40

Reference:

Thall, Peter F., Simon, R. and Estey, E.H. "Bayesian sequential monitoring designs for single-arm clinical trials with multiple outcomes," Statistics in Medicine 14:357-379, 1995.

**11.1** In an update of the data on October 6, 2010, 12 of the first 21 patients treated (57%) had achieved CR or Cri. This was achieved with minimal drug related side effects, and allowed several patients to proceed safely to allogeneic stem cell transplant. These data are very encouraging and if consistent in a larger number of patients may show that single agent CMC-544 therapy is superior to standard combination intensive chemotherapy with regard to safety and efficacy. We therefore propose to increase the total number of patients treated to 60 patients to allow a more accurate assessment of the response rate and to define more precisely predictive

factors for response and outcome with CMC-544 therapy. The analysis of predictive factors for response, durability of response, and survival will be conducted using standard statistical methods, and will be descriptive, for the purpose of guiding future large scale and pivotal trials with CMC-544 in ALL.

**11.2** Following the update of January 7, 2011, it is proposed to treat 20 patients with a weekly schedule of CMC-544, to gain experience with efficacy and toxicity. This portion of the study should protect against an overall response rate < 40%. Therefore the study will stop early if the number of responses over number evaluable is: 0/7, 1/10, 2/14, and 3/17. Otherwise a total of 20 patients will be treated. The response and toxicity evaluations will be descriptive.

**11.3** Following an update on December 2, 2011, the weekly schedule was assessed to demonstrate equal or better efficacy and perhaps less toxicity than the single dose every 3-4 weeks. In the first 15 evaluable patients, 8 (53%) achieved marrow CR. An additional 20 patients will be treated for a total of 40 patients to assess more precisely the response and toxicity rates with the weekly schedule.

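### Section 11 was only partly updated after the sample size grew: the total of 60 does not fit the cohorts, the stopping table is for 40 patients, and the weekly rule covers 20 of 40

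*Combined protocol and SAP*

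**What the plan says.** - **Section 11.0** gives the size: "A total of up to 60 patients will be treated". Its futility rule opens "The trial will be stopped early if" and requires the posterior probability of a response rate above 0.20 to be under 0.10, with a beta(1,1) prior. The boundaries are "0/10, 1/17, 2/24, 3/31, 4/37".
- **The operating-characteristics table** gives early-stopping probabilities of 0.79, 0.24 and 0.044 at true rates 0.1, 0.2 and 0.3. The sample-size percentiles are 10/17/37, 40/40/40 and 40/40/40.
- **Section 11.1** (October 2010) proposes to "increase the total number of patients treated to 60 patients".
- **Section 11.2** (January 2011) adds a weekly-schedule cohort. It says "This portion of the study should protect against an overall response rate < 40" (a percentage), lists boundaries 0/7, 1/10, 2/14 and 3/17, and ends "Otherwise a total of 20 patients will be treated".
- **Section 11.3** (December 2011) says "An additional 20 patients will be treated for a total of 40 patients". It gives no further boundaries.
- **Section 2.5** (January 2011, where the weekly schedule is introduced) says "At the present update, 38 patients have been treated", with 18 responses in 32 evaluable.
- **Section 2.6** (December 2011) counts 49 patients on the single dose, reports the first 20 weekly patients as fully accrued, and records agreement to add 20 more.
- **Section 5.2.2** still gives 20 weekly patients and points to Section 2.4 for the background.

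**The concern.** The statistical section should let a reader find three things: the maximum number of patients, the stopping rule for each group, and the properties of that rule at that maximum. Here the 60 was set before the weekly schedule existed and is printed without a schedule label. The table beside it stops at 40. The weekly rule was written for a cohort that has since doubled. In addition, Section 11.2 ties its rule to the weekly portion, but Section 11.0 speaks of the trial as a whole, so it is unclear whether the 20% rule covers the single-dose patients or both schedules. At stake are the stated enrolment ceiling and the monitoring of the weekly cohort, the only one that Section 11.3 enlarges.

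**Working it through.** **1. Cohort totals** (inputs from Sections 2.5, 2.6, 11.0 and 11.3)

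- Treated or accrued by December 2011: 49 + 20 = 69, above 60.
- Planned: 49 + 40 = 89.
- If 60 is the single-dose cap alone: 60 + 40 = 100.
- If 60 is the trial total: 60 − 40 = 20 single-dose patients, but 38 had been treated when the weekly schedule was introduced.

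No reading makes 60 the total.

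**2. Boundaries of the Section 11.0 rule**

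With a beta(1,1) prior and x responses in n patients, the posterior is beta(1+x, 1+n−x), so Pr(θ > 0.20 | data) = Pr(Bin(n+1, 0.20) ≤ x). For each x, find the smallest n that brings this below 0.10.

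| x/n | Posterior | One patient earlier |
|---|---|---|
| 0/10 | 0.086 | 0.107 |
| 1/17 | 0.099 | 0.118 |
| 2/24 | 0.098 | 0.115 |
| 3/31 | 0.093 | 0.107 |
| 4/37 | 0.099 | 0.112 |
| 5/44 | 0.090 | 0.102 |
| 6/50 | 0.092 | 0.103 |

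The five printed boundaries are reproduced exactly. Beyond 4/37 the criterion continues 5/44, 6/50, 7/56 (to 60), then 8/62, 9/68, 10/74, 11/80, 12/85 (to 89), then 13/91, 14/97 (to 100).

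**3. Operating characteristics**

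Exact recursion: let f(n, x) be the probability of reaching n patients with x responses without having stopped. Then f(n+1, x) = (1−p)·f(n, x) + p·f(n, x−1), and any mass at or below the boundary is removed and counted as stopped.

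| Maximum | Stop at p = 0.1 | 0.2 | 0.3 | Percentiles at 0.1 | at 0.2 | at 0.3 |
|---|---|---|---|---|---|---|
| Printed | 0.79 | 0.24 | 0.044 | 10/17/37 | 40/40/40 | 40/40/40 |
| 40 | 0.783 | 0.240 | 0.045 | 10/17/37 | 40/40/40 | 40/40/40 |
| 60 | 0.886 | 0.276 | 0.047 | 10/17/37 | 44/60/60 | 60/60/60 |
| 89 | 0.960 | 0.316 | 0.047 | 10/17/37 | 44/89/89 | 89/89/89 |
| 100 | 0.973 | 0.328 | 0.047 | 10/17/37 | 44/100/100 | 100/100/100 |

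The printed table is reproduced at 40: all nine percentiles match and the probabilities agree to within 0.01. If the maximum is raised to 60 and no boundary is added after 4/37, the stopping probabilities stay at 0.783/0.240/0.045, but the percentiles at 0.2 and 0.3 become 60/60/60. Either way the printed table does not describe 60.

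**4. Can the Section 11.0 rule still stop the trial?**

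Section 2.5 gives 18 responses. The boundary is 12 at a maximum of 89 and 14 at 100. With no further response, the rule would first stop at n = 120 (posterior 0.094). At 18/100 the posterior is 0.34. So it cannot stop the trial at any maximum considered here.

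**5. Weekly rule**

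Applying the same recursion to 0/7, 1/10, 2/14 and 3/17 gives stopping probabilities of 0.085, 0.272 and 0.614 at true rates 0.40, 0.30 and 0.20. These are identical for a maximum of 20 or 40, because no boundary lies beyond 17. At 8 of 15 responding (Section 11.3), the count already exceeds 3, so the listed rule can no longer stop the cohort.

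Section 11.2 gives no prior or cutoff, so extending it to 40 needs an assumption. Five criteria of the form Pr(θ > 0.40 | data) < c reproduce the four boundaries; others may too:

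- beta(0.3, 0.7) with c = 0.02, and beta(1,1) with c = 0.036, both monitored from patient 7;
- beta(2,3) with c = 0.046;
- beta(4,6) with c = 0.070 or 0.071.

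Run to 40, they stop with probability 0.12–0.17, 0.44–0.57 and 0.87–0.94 at true rates 0.40, 0.30 and 0.20. Starting from 8/15, the chance of a later stop is 0.05–0.25 if the remaining patients respond at 0.20, and below 0.04 at 0.30 or more.

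**The case against.** Sections 11.1 to 11.3 are dated updates. Read in order, 11.3 openly replaces the 20 in 11.2 with 40. That stands, and the 20 in 11.2 is not by itself an error. It does not rescue the unlabelled 60 in Section 11.0, the 40-patient table or the 20 in Section 5.2.2, all of which are operative text.

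A reader can also assemble 49 + 40 from Section 2.6 and take 60 as a single-dose cap that 49 respects. That is a fair reading, but Section 11.0 does not state it. The 100-patient case is the weakest, because it needs 60 − 49 = 11 more single-dose patients that Section 2.6 does not mention.

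The strongest point is that recalculated properties describe a rule that can no longer stop anything, and that no printed calculation is wrong for its own maximum. Both statements are true. They limit the consequence, but they do not make the stated maximum and table those of the current plan. Whether to extend weekly monitoring is likewise a design choice, since Section 11.2 calls its evaluations descriptive. The defect is that the plan does not record the choice.

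**Conclusion.** The concern holds. The total of 60 is contradicted by 69 patients already treated or accrued and 89 planned (100 on the alternative reading). The table belongs to a maximum of 40. At 60, the stopping probability is about 0.10 higher at a true rate of 0.1 (0.886 − 0.783) and about 0.04 higher at 0.2 (0.276 − 0.240), and almost unchanged at 0.3. The scope of the Section 11.0 rule and the monitoring of the second 20 weekly patients are not stated.

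The practical effect is small. The Section 11.0 rule cannot stop the trial, and a weekly stop after 8/15 is unlikely unless the response rate falls sharply. The main-rule figures rest only on the plan's own criterion and prior. Those for 89 and 100 also assume one response rate across both schedules. The figures for an extended weekly rule rest on assumed criteria and are given as a range for that reason.

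**What to change.** 1. In Section 11.0, state the sponsor-confirmed maximum for each schedule and in total.
2. Change the 20 in Section 5.2.2 to agree with Section 11.3, mark the 20 in Section 11.2 as superseded, and redirect the reference to Section 2.4 to Sections 2.5 and 2.6.
3. Say which patients the Section 11.0 rule covers, and replace its table and boundary list at that maximum. For 60, add 5/44, 6/50 and 7/56. For the whole trial at 89, also add 8/62, 9/68, 10/74, 11/80 and 12/85. For 100, also add 13/91 and 14/97. The matching table rows are in the check above. Only the one that applies is needed.
4. In Sections 11.2 and 11.3, either state that weekly monitoring ended with the first 20 patients, or give the prior, cutoff, boundaries and operating characteristics to 40. No extended weekly boundaries are proposed here, because several criteria fit the four that are listed.

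The cost is a few sentences and one short table, with a second table only if weekly monitoring continues. No patients are added beyond those already planned in Section 11.3.
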